8.4.1	Sponsor-Investigator Reporting, Notifying Mayo IRB.....	27
8.4.2	Sponsor-Investigator Reporting: Notifying the FDA.....	27
8.5	UNBLINDING PROCEDURES	28
8.6	STOPPING RULES.....	28
8.7	MEDICAL MONITORING	28
8.7.1	Internal Data and Safety Monitoring Board	28
8.8	CONFIDENTIALITY.....	29
8.9	SOURCE DOCUMENTS.....	29
8.10	CASE REPORT FORMS	29
8.11	RECORDS RETENTION	30
9	STUDY MONITORING, AUDITING, AND INSPECTING	30
9.1	STUDY MONITORING PLAN	30
9.2	AUDITING AND INSPECTING	31
10	ETHICAL CONSIDERATIONS	31
11	STUDY FINANCES	31
11.1	FUNDING SOURCE	31
11.2	SUBJECT STIPENDS OR PAYMENTS	31
12	PUBLICATION PLAN	31
13	REFERENCES	32

LIST OF ABBREVIATIONS

AE	Adverse Event/Adverse Experience
BMI	Body Mass Index
CFR	Code of Federal Regulations
CRF	Case Report Form
DSMB	Data and Safety Monitoring Board
EUS	Endoscopic Ultrasound
FDA	Food and Drug Administration
GCP	Good Clinical Practice
HIPAA	Health Insurance Portability and Accountability Act
IDE	Investigational Device Exemption
IGB	Intragastric Balloon
IRB	Institutional Review Board
MRE	Magnetic Resonance Elastography
MRS	Magnetic Resonance Spectroscopy
NAFLD	Non-alcoholic Fatty Liver Disease
NAS	Non-alcoholic Steatohepatitis Score
NASH	Non-alcoholic Steatohepatitis
PHI	Protected Health Information
PI	Principal Investigator
SAE	Serious Adverse Event/Serious Adverse Experience
SOP	Standard Operating Procedure
TBWL	Total Body Weight Loss
UADE	Unanticipated Adverse Device Effect

Study Summary

Title	A Pilot Combined Endoscopic Ultrasound Guided Core Liver Biopsy and Intragastric Balloon Placement for Management of Nonalcoholic Steatohepatitis and Obesity
Running Title	EUS and IGB for Management of NASH and Obesity
IRB Protocol Number	15-009262
Phase	Pilot
Methodology	Open Label

Overall Study Duration	60-64 Weeks
Subject Participation Duration	12 months
Objectives	Significant weight loss achieved with the IGB in NASH patients with BMI between 30 – 55 kg/m ² and early fibrosis based on MRE is associated with ≥ 2 points improvement in NAS and regression of fibrosis on paired EUS guided liver core biopsies.
Number of Subjects	25
Diagnosis and Main Inclusion Criteria	Inclusion criteria to our study include NASH patients with evidence of early fibrosis (excluding advanced fibrosis or cirrhosis) by baseline liver biopsy when available, and/or MRE (magnetic resonance elastography), who are referred for an intragastric balloon placement for weight loss.
Study Device	Orbera Intragastric Balloon (Apollo Endosurgery Austin, TX)
Duration of Exposure	6 months
Statistical Methodology	We have the resources to enroll at total of 20 patients (additional 5 in case of early withdrawal) to this study. With a sample size of 20 we will have 80% power to detect a medium to large (effect size 0.66) improvement in NASH activity scores on paired liver biopsies using a paired t-test with a two sides p-value < 0.05. The table below shows that sample size needed to detect small, medium, or large improvement in NAS scores on paired liver biopsies at 80% power.

1 Introduction

This document is a protocol for a human research study. This study will be carried out in accordance with the procedures described in this protocol, applicable United States government regulations and Mayo Clinic policies and procedures.

1.1 Background

Obesity has reached pandemic proportions.[1] Mirroring this rise in obesity prevalence is a rise in its associated co-morbid conditions including metabolic syndrome and non-alcoholic fatty liver disease (NAFLD). [2] Indeed, NAFLD is thought to afflict about 70% and 50% of obese adults and children, respectively.[3] Of those, about 5% will progress to cirrhosis and end stage liver disease. Non-alcoholic steatohepatitis (NASH) is projected to be the leading cause of liver transplantation in the United States by 2020. [4]

Hepatic fibrosis regardless of etiology progresses to cirrhosis if the etiological agent is not removed or treated. [5] There is growing evidence for reversibility of steatohepatitis and hepatic fibrosis especially in early stages and with significant weight loss. [5] In a seminal study of 293 patients with histologically proven NASH who had life-style modification to reduce their weight over 52 weeks, 72 (25%) achieved resolution of steatohepatitis, 138 (47%) had reductions in nonalcoholic fatty liver disease activity score (NAS), and 56 (19%) had regression of fibrosis. [5] The degree of weight loss was independently associated with improvements in all NASH-related histologic parameters with all patients who lost $\geq 10\%$ of their total body weight (%TBWL) had reductions in NAS, 90% had resolution of NASH, and 45% had regression of fibrosis, compared to 32% (reduction in NAS), 10% (resolution of NASH), and 16% (regression of fibrosis) in those who lost $\leq 5\%$. Life-style interventions for obesity; however, are associated with poorly sustained effects and relatively weak efficacy. Indeed, in this study less than 10% of the cohort achieved $\geq 10\%$ TBWL with life-style modification alone and the majority (70%) achieved less than 5% TBWL.[5]

The Orbera™ Intra-gastric Balloon (Apollo Endosurgery, Austin, TX), previously known as the BioEnterics Intra-gastric Balloon (BIB) (Allergan, Irvine, CA) is an elastic spherical balloon made from silicone, filled with about 600 ml of saline and is placed in the stomach via upper endoscopy. This IGB is designed to stay in place for 6 months prior to endoscopic removal and has been widely used in Europe, South America, and the Middle East with excellent safety profile. In an ASGE Bariatric Endoscopy Task Force systematic review and meta-analysis the pooled %TBWL after the Orbera IGB implantation was 12.3% (95% CI, 7.91–16.73), 13.16% (95% CI, 12.37–13.95), and 11.27% (95% CI, 8.17–14.36) at 3, 6, and 12 months after implantation, respectively.[6] This was based on a review of 55 studies. This balloon is currently FDA approved for use in the United States after a US randomized multicenter pivotal trial demonstrated similar efficacy.

The rates of adverse events after implantation of the Orbera balloon are pooled from a manual review of 68 studies (8500 implantations) and are summarized in Figure 1. Pain and nausea are frequent side-effects after Orbera balloon implantation, occurring in up to 33.7% of subjects. Medications such as proton pump inhibitors, antispasmodic drugs, and antiemetics are usually prescribed prophylactically before, during, and after balloon

placement to prevent or minimize these expected common side effects. Serious side-effects with Orbera balloon are rare with an incidence of migration and gastric perforation of 1.4% and 0.1%, respectively. Most of the reported perforations with the Orbera were in patients who had undergone previous gastric surgeries, which is a contraindication for use in the US.[6]

More particularly, the safety and efficacy of the Orbera intragastric balloon has been previously demonstrated in patients with suspected NASH. A small study randomized 18 obese or overweight patients with histologically proven nonalcoholic steatohepatitis (NASH) to lifestyle modification plus Orbera balloon placement or to lifestyle modification plus a sham procedure. Weight and liver histology were assessed before and 6 months after balloon insertion or the sham procedure. The Orbera balloon placement group had a significantly higher reduction in mean BMI (1.52 vs 0.8; $P = .0008$) and a superior improvement in nonalcoholic fatty liver disease activity scores at the end of treatment (2 [SD 0.75] vs 4 [SD 2.25]; $P = .03$).[7] Three other single arm studies demonstrated improvement in liver steatosis by cross sectional imaging and liver biochemical testing with the Orbera balloon in patient with suspected NASH. [8-10]

The detection of early fibrosis with steatohepatitis is critical given the more aggressive nature of disease, which requires a more aggressive treatment plan. However, early fibrosis is difficult to diagnose with non-invasive imaging modalities without the need for a liver biopsy. Although modalities such as transient elastography (Fibroscan) have good diagnostic accuracy for cirrhosis, its performance is suboptimal for earlier stages of fibrosis. [11] Several studies have established that liver magnetic resonance elastography (MRE) is an accurate technique for the detection of earlier stages of liver fibrosis and steatosis. MRE has therefore emerged as a potential alternative to liver biopsy in establishing the diagnosis of NASH. [12, 13] **However, despite MRE accuracy in establishing the diagnosis, there are no studies to demonstrate its sensitivity to change in response to an intervention such as weight loss. Furthermore, there are no standardized validated criteria to objectively assess improvement in NASH and fibrosis with MRE as exit for liver biopsy, which remains the gold standard in clinic trial evaluating the impact of intervention on NASH.**[14]

Endoscopic ultrasound guided liver biopsy has been shown to be very safe and capable of adequately and reproducibly sampling widely separated liver regions under direct guidance; thus yielding more representative and suitable liver tissue for the staging and histopathological follow-up of NASH, especially in the confounds of clinical trial.[15-17] EUS-guided core liver biopsy can produce equal or higher number of complete portal tracts compared to traditional percutaneous approach, while avoiding sampling error in a paired liver biopsy design (pre and post intervention), which is currently a pitfall of the precautionous liver biopsy approach given the patchy nature of non-alcoholic fatty liver disease. [18]

Given the limited data of the impact of weight loss produced by the intragastric balloon on NASH with early fibrosis, we propose a prospective study to evaluate the impact of weight loss produced the Orbera intragastric balloon on objective NASH histopathological parameters.

1.2 Investigational Device

The Orbera (Apollo Endosurgery, Austin Tx) is an elastic spherical balloon made of silicone, filled with 450 to 700 mL of saline solution, and is FDA approved for weight loss in adult US patients with body mass index between 30 to 40 kg/m². The deflated balloon comes preloaded on a catheter, which is blindly advanced transorally into the stomach. An endoscope is then advanced alongside it to ensure accurate placement of the balloon in the fundus. Under direct visualization, the balloon is then inflated by injecting saline solution through the external portion of the catheter. The Orbera balloon is currently used in many countries outside the United States and is typically implanted for 6 months and then retrieved endoscopically.

1.3 Preclinical Data

See PMA study of the Orbera intragastric balloon

1.4 Clinical Data to Date

The Orbera™ Intragastric Balloon (Apollo Endosurgery, Austin, TX), previously known as the BioEnterics Intragastric Balloon (BIB) (Allergan, Irvine, CA) is an elastic spherical balloon made from silicone, filled with about 600 ml of saline and is placed in the stomach via upper endoscopy. This IGB is designed to stay in place for 6 months prior to endoscopic removal and has been widely used in Europe, South America, and the Middle East with excellent safety profile. In an ASGE Bariatric Endoscopy Task Force systematic review and meta-analysis the pooled %TBWL after the Orbera IGB implantation was 12.3% (95% CI, 7.91–16.73), 13.16% (95% CI, 12.37–13.95), and 11.27% (95% CI, 8.17–14.36) at 3, 6, and 12 months after implantation, respectively.[6] This was based on a review of 55 studies. This balloon is currently FDA approved for use in the United States after a US randomized multicenter pivotal trial demonstrated similar efficacy.

The rates of adverse events after implantation of the Orbera balloon are pooled from a manual review of 67 studies (8500 implantations) and are summarized in Figure 1. Pain and nausea are frequent side-effects after Orbera balloon implantation, occurring in up to 33.7% of subjects. Medications such as proton pump inhibitors, antispasmodic drugs, and antiemetics are usually prescribed prophylactically before, during, and after balloon placement to prevent or minimize these expected common side effects. Serious side-effects with Orbera balloon are rare with an incidence of migration and gastric perforation of 1.4% and 0.1%, respectively. Most of the reported perforations with the Orbera were in patients who had undergone previous gastric surgeries, which is a contraindication for use in the US.[6]

More particularly, the safety and efficacy of the Orbera intragastric balloon has been previously demonstrated in patients with suspected NASH. A small study randomized 18 obese or overweight patients with histologically proven nonalcoholic steatohepatitis (NASH) to lifestyle modification plus Orbera balloon placement or to lifestyle modification plus a sham procedure. Weight and liver histology were assessed before and 6 months after balloon insertion or the sham procedure. The Orbera balloon placement group had a significantly

higher reduction in mean BMI (1.52 vs 0.8; $P = .0008$) and a superior improvement in nonalcoholic fatty liver disease activity scores at the end of treatment (2 [SD 0.75] vs 4 [SD 2.25]; $P = .03$). [7] Three other single arm studies demonstrated improvement in liver steatosis by cross sectional imaging and liver biochemical testing with the Orbera balloon in patient with suspected NASH. [8-10]

1.5 Study Rationale and Risk/Benefits

1.5.1 Study Rationale

NASH with early fibrosis is serious condition that afflicts a significant portion of patients with obesity with the potential to progress to cirrhosis. Weight loss of $\geq 10\%$ TBWL has been definitively shown to be an effective treatment of NASH with regression of early fibrosis, however, this magnitude of weight loss is only achieved in the minority ($\leq 10\%$) of patients with life style modification. The IGB achieves a mean %TBWL weight loss of about 13% at 6 months, and has previously shown efficacy in management of NASH in a small cohort outside the US. In 8 patients with biopsy proven NASH and obesity, who underwent the Orbera IGB placement and paired percutaneous liver biopsies before and 6 months after Orbera placement, the NAS significantly improved with IGB placement group compared to the life-style intervention alone (4 ± 2.25 vs. 2 ± 0.75 vs. $P = .03$). However, this study demonstrated no improvement in fibrosis scores as only the minority of the cohort had true early fibrosis. From a recent seminal paper we know that achieving $\geq 10\%$ TBWL is clearly associated with regression in fibrosis, although this magnitude of weight loss is difficult to achieve with life-style modification only. Thus, in this protocol we will be selecting patients with NASH and early fibrosis diagnosed by MRE for placement of intragastric balloon and concomitant EUS guide liver biopsies at the time of balloon placement and removal (6 months after) to evaluate the impact of weight loss achieved by the Orbera IGB on NAS and fibrosis regression.

The use of paired EUS guided liver biopsies is crucial for our study design as despite MRE accuracy in establishing the diagnosis of NASH with early fibrosis for patient inclusion to our study, there are no studies to demonstrate its sensitivity to change in response to an intervention such as weight loss. Furthermore, there are no standardized validated criteria to objectively assess improvement in NASH and fibrosis with MRE as exists for liver biopsy, which remains the gold standard in clinic trial evaluating the impact of intervention on NASH.

Spectroscopic and biochemical hepatic fat quantitative assessment pre- and post-intervention – Rationale:

The degree of lipid saturation and polyunsaturation can be measured noninvasively by proton magnetic resonance spectroscopy [19]. This technique adds no cost, as the series can be simultaneously captured during MRE acquisition session, adding few minutes to the procedure. Evidence suggests that depletion of hepatic polyunsaturated fatty acids (PUFAs) reduces hepatic fatty acid oxidation and triglyceride export. Furthermore, it is associated with augmentation in in hepatic fatty acid and triglyceride synthesis, leading to increased triglyceride aggregation. Moreover, this process has been thought to increase inflammation and facilitates the development of steatohepatitis. Indeed, studies have shown that alterations

in tissue lipid saturation may portend sinister clinical outcomes more reliably than simple means of fatness measurements [20].

To the best of our knowledge, no studies have corroborated the sensitivity of H-MRS detection of SI and PUI changes, as well as other indices of hepatic lipid composition, with weight loss, and its correlation to decrease in total steatosis, changes in liver stiffness, as well as changes in fibrosis scores on histology.

Our current study offers a rare window to accurately examine and capture these changes due to the availability of liver tissue histology pre- and post-intervention. This will allow the determination H-MRS reliability in predicting lipidomic analysis changes in a NASH afflicted liver, obviating the need of invasive testing.

Furthermore, an unmet need in the understanding of nonalcoholic fatty liver disease is the determination of the interactions between the changes in hepatic lipid polyunsaturated fatty acids (PUFA) depletion and liver injury; considering the expected improvement in liver histology parameters with our proposed intervention, our study would offer a unique opportunity to correlate these improvements with PUFA depletion[19, 21, 22].

1.5.2 Anticipated Risks

The rates of adverse events after implantation of the Orbera balloon are pooled from a manual review of 68 studies (8500 implantations) and are summarized in Figure 1. Pain and nausea are frequent side-effects after Orbera balloon implantation, occurring in up to 33.7% of subjects. Medications such as proton pump inhibitors, antispasmodic drugs, and antiemetics are usually prescribed prophylactically before, during, and after balloon placement to prevent or minimize these expected common side effects. Serious side-effects with Orbera balloon are rare with an incidence of migration and gastric perforation of 1.4% and 0.1%, respectively. Most of the reported perforations with the Orbera were in patients who had undergone previous gastric surgeries, which is a contraindication for use in the

US.[6]

[figure not shown]

Figure 1. Pooled Orbera Complications from 68 studies (8500 patients) [6]

More particularly, the safety of the Orbera intragastric balloon has been previously demonstrated in patients with suspected NASH. A small study randomized 18 obese or overweight patients with histologically proven nonalcoholic steatohepatitis (NASH) to lifestyle modification plus Orbera balloon placement or to lifestyle modification plus a sham procedure. Weight and liver histology were assessed before and 6 months after balloon insertion or the sham procedure. The Orbera balloon placement group had a significantly higher reduction in mean BMI (1.52 vs 0.8; $P = .0008$) and a superior improvement in nonalcoholic fatty liver disease activity scores at the end of treatment (4 [SD 2.5] vs 2 [SD 20.75]; $P = .03$), with no increased incidence of adverse events.[7] Three other single arm studies demonstrated improvement in liver steatosis by cross sectional imaging and liver biochemical testing with the Orbera balloon in patient with suspected NASH with excellent safety profile in these cohorts with suspected NASH. [8-10]

EUS guided core liver biopsy has been established as a safe, adequate, and cost effective mean to obtain diagnostic liver tissue to diagnose and stage chronic liver disease. In more than 200 patients reported in the literature, EUS guided liver biopsy was capable in providing similar or more adequate liver sample than percutaneous or trans-jugular approach with no reported incidence of any adverse events. [15-17, 23] Our EUS group has conducted over 800 EUS guided liver biopsies, with no reported incidence of immediate or delayed adverse events. In this protocol using paired EUS guided liver biopsies at the time of balloon insertion and removal will be cost effective, safe, only add few extra minutes to the procedure, and will allow us to minimize sampling error and isolate the effects of weight loss achieved by the intragastric balloon on gold standard histological endpoints.

1.5.3 Potential Benefits

Hepatic fibrosis regardless of etiology progresses to cirrhosis if the etiological agent is not removed or treated. [5] There is growing evidence for reversibility of steatohepatitis and hepatic fibrosis especially in early stages and with significant weight loss. [5] In a seminal study of 293 patients with histologically proven NASH who had life-style modification to reduce their weight over 52 weeks, 72 (25%) achieved resolution of steatohepatitis, 138 (47%) had reductions in nonalcoholic fatty liver disease activity score (NAS), and 56 (19%) had regression of fibrosis. [5] The degree of weight loss was independently associated with improvements in all NASH-related histologic parameters with all patients who lost $\geq 10\%$ of their total body weight (%TBWL) had reductions in NAS, 90% had resolution of NASH, and 45% had regression of fibrosis, compared to 32% (reduction in NAS), 10% (resolution of NASH), and 16% (regression of fibrosis) in those who lost $\leq 5\%$. Life-style interventions for obesity; however, are associated with poorly sustained effects and relatively weak efficacy. Indeed, in this study less than 10% of the cohort achieved $\geq 10\%$ TBWL with life-style modification alone and the majority (70%) achieved less than 5% TBWL.[5]

The Orbera intragastric balloon is expected to results in 12.3% (95% CI, 7.91–16.73), 13.16% (95% CI, 12.37–13.95), and 11.27% (95% CI, 8.17–14.36) TBWL at 3, 6, and 12 months after implantation, respectively.[6] This was based on a review of 55 studies. This balloon is currently FDA approved for use in the United States after a US randomized multicenter pivotal trial demonstrated similar efficacy. Thus, with the anticipated weight loss seen with the Orbera Intragastric balloon, we expect improvement in histological NASH parameters and regression of fibrosis with the weight loss achieved with the intragastric balloon.

The ability to quantify and capture hepatic fat change, and correlate it to spectroscopic changes could offer important non-invasive means of NASH progression/regression in afflicted individuals. This study would offer a unique opportunity to corroborate the utility of MRS in accurate and reliable evaluation of this parameter.

2 Study Objectives

2.1 Primary Objective

NASH with early fibrosis is serious condition that afflicts a significant portion of patients with obesity with the potential to progress to cirrhosis. Weight loss of $\geq 10\%$ TBWL has been definitively shown to be an effective treatment of NASH with regression of early fibrosis, however, this magnitude of weight loss is only achieved in the minority ($\leq 10\%$) of patients with life style modification. The IGB achieves as mean %TBWL of 13%. Therefore, we aim to study the impact of weight loss achieved by the Orbera intragastric balloon on NAS and liver fibrosis in a cohort selected by MRE to have NASH with early fibrosis but not cirrhosis. This will be assessed with a paired EUS guided biopsies at the time of balloon placement and removal after six months.

Hypothesis 1: Significant weight loss achieved with the IGB in NASH patients with BMI between 30 – 55 kg/m² and fibrosis based on MRE is associated with ≥ 2 points improvement in NAS and regression of fibrosis on paired EUS guided liver core biopsies.

[figure not shown]

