3.2 Primary Study Endpoint

Number of subjects with ≥ 2 points improvement in NASH activity scores on paired liver biopsies before and 6 months after intragastric balloon placement.

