3.3 Secondary Study Endpoints

- Regression of fibrosis on paired EUS guided liver core biopsies.

- Percent total body weight loss at 6 months after Orbera balloon placement.
- Obtaining lipid saturation (SI) and polyunsaturation (PUI) indices via H-MRS technology pre- and post-intervention
- Obtaining hepatic triglycerides content (HTGC) via H-MRS technology pre- and post-intervention.
- Obtaining percent unsaturated fatty acyl chains present in this cohort of NASH patients, as well as changes that occur in the setting of weight loss.
- Obtaining percent polyunsaturated fatty acyl chains present in this cohort of NASH patients, as well as changes that occur in the setting of weight loss.
- Measurement of hepatic lipid composition by needle biopsy and lipidomic analysis techniques before and after weight loss.
- Correlation of MRS obtained lipid composition to lipidomic analysis composition

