6.3 Tissue lipidomics workup

A total of 50 mg of liver tissue will be collected via EUS-guided biopsy. Sharkcore needle is 22 gauge. Diameter is ~0.7 mm. ~270 mm of tissue length will be acquired and will deliver a volume of ~50 mg. The sample will be frozen in liquid nitrogen immediately upon harvesting in the endoscopy suite and placed in a 1.5 conical Eppendorf tube. Samples shall not sit more than few minutes before flash freezing to ensure adequate analysis. Also, inspection before freezing will occur to ensure that the tissue is relatively clean specimen on inspection.

7 Statistical Plan

Baseline subject characteristics will be described by their means, medians and and/or frequencies. For our primary study endpoint of improvement in NASH activity scores on paired liver biopsies at baseline and after 6 months, we will be using a paired t-test with two sided alpha <0.05. With a sample size of 20 subjects, we will have 80% power to detect a medium to large difference in activity scores (0.66). Please see table below for minimum sample size needed for each desired effect size.

	Small effect size 0.5	Medium effect size 0.66	Large effect size 0.8
Sample (N)	34	20	15

Additionally, we will run a linear regression analysis with the change in NASH activity scores as the outcome with baseline BMI and diabetes as the covariates on a univariable and multivariable fashion to investigate their effects on the primary outcome.

For our secondary endpoint of number of subjects with regression of fibrosis in paired liver biopsies, we will be reporting the percentage of subjects with regression. As far as the secondary endpoint of percent total body weight 6 months after Orbera balloon placement, we will be reporting the mean or median percent total body weight loss at 6 months.

For our secondary endpoint of quantifying total fat liver and triglycerides content, we will be reporting the mean and median percent of change at 6 months.

8 Safety and Adverse Events

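### The plan reports fibrosis, half of the primary hypothesis, in one direction only and never alongside NAS response

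*Combined protocol and SAP*

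**What the plan says.** - **Section 2.1, aim:** "we aim to study the impact of weight loss achieved by the Orbera intragastric balloon on NAS and liver fibrosis".
- **Section 2.1, Hypothesis 1** (repeated under Objectives in the Study Summary): the weight loss is "associated with ≥ 2 points improvement in NAS and regression of fibrosis on paired EUS guided liver core biopsies".
- **Section 3.2, primary endpoint:** "Number of subjects with ≥ 2 points improvement in NASH activity scores on paired liver biopsies before and 6 months after intragastric balloon placement". Fibrosis is not mentioned.
- **Section 3.3, first secondary endpoint:** "Regression of fibrosis on paired EUS guided liver core biopsies".
- **Section 7, NAS:** "we will be using a paired t-test with two sided alpha <0.05", plus a linear regression of NAS change on baseline BMI and diabetes.
- **Section 7, fibrosis:** "we will be reporting the percentage of subjects with regression".
- **Section 4.4.1:** progression to cirrhosis is a reason for withdrawal, and up to 5 subjects withdrawn for reasons other than severe adverse events may be replaced. The plan does not say how a subject withdrawn for cirrhosis enters the fibrosis result.

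The protocol contains no joint endpoint, no cross-tabulation of the two changes and no report of fibrosis worsening.

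**The concern.** The primary objective names two histological effects, and the two are handled unequally. NAS gets a definition, a test and a power statement. Fibrosis gets one percentage, which counts only subjects who moved in the hoped-for direction.

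Two things are lost. First, separate results for NAS and fibrosis do not determine how many subjects had both changes, which is what Hypothesis 1 describes if it is meant per subject. Second, an impact on fibrosis includes harm. A percentage regressed does not separate the remaining subjects into unchanged and worse. Under Section 3.2, a subject who gains 2 NAS points while fibrosis advances by a stage is a responder, and no planned output would show it.

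The protocol itself gives reason to expect the two measures to diverge. Section 1.5.1 says that the earlier balloon study improved NAS without improving fibrosis scores, attributes this to few patients having true early fibrosis, and selects the present cohort accordingly. Whether NAS and fibrosis now move together is therefore close to the reason for the trial.

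**Working it through.** **1. The plan's own figure.** Inputs from Section 7: N = 20, standardized effect 0.66, two-sided alpha 0.05. For a paired t-test, the noncentrality is 0.66 × √20 = 2.95 on 19 degrees of freedom, and the power is 79.95%. The stated 80% reproduces. The other entries in the table also hold: effect 0.5 with N = 34 gives 80.8%, and effect 0.8 with N = 15 gives 82.1%. This power concerns mean NAS change only. It covers neither the responder count, nor fibrosis, nor the two together.

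**2. What the NAS test shows about 2-point responders.** With N = 20 the test is significant once the observed mean change exceeds 2.093/√20 = 0.468 SD. The protocol gives no SD for the change. Assuming 1 to 3 points, the threshold is a mean change of 0.47 to 1.40 points. A significant result is therefore possible with a mean change below 2 points, and it does not yield the Section 3.2 count.

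**3. What separate figures show about both changes.** If a subjects respond on NAS and b regress, out of n, the number with both lies between max(0, a + b − n) and min(a, b).

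| Inputs | Lower bound | If independent | Upper bound |
|---|---|---|---|
| 60% NAS response (assumed), 45% regression (cited for ≥10% weight loss) | 12 + 9 − 20 = 1 | 0.60 × 0.45 × 20 = 5.4 | 9 |
| 47% and 19% (overall rates in the cited lifestyle study) | 0 | 0.47 × 0.19 × 20 = 1.8 | 3.8 |

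The 47% is for NAS reduction of any size, so the rate of improvement by at least 2 points may be lower. As Section 7 stands, even the value of a is not a planned output.

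**4. What the percentage regressed shows about worsening.** If 9 of 20 regress, 20 − 9 = 11 do not, and between 0 and 11 of those may be worse.

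**5. Divergence in the protocol's own sources.** In the lifestyle study (Section 1.1), 138 patients had a NAS reduction and 56 had fibrosis regression. Even if all 56 were among the 138, at least 138 − 56 = 82 of 138 (59%) had a NAS reduction without regression. Among those losing at least 10%, all had a NAS reduction and 45% regressed, so 55% did not. The protocol does not say how many of these worsened.

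**6. Chance of seeing a responder who worsened.** The documents give no rate. Assume 12 NAS responders, each with probability q of worse fibrosis. Then P(at least one) = 1 − (1 − q)^12, which is 46% for q = 5%, 72% for q = 10% and 93% for q = 20%.

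**7. Precision of the added figures.** The exact 95% interval for 9 of 20 is 23.1% to 68.5%. For 0 of 20 it is 0% to 16.8%, so even an empty worse category would leave sizeable uncertainty. That is why intervals should accompany the counts.

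**The case against.** The strongest reply is that Hypothesis 1 is a cohort statement. It speaks of association, never mentions the same subject, and follows an aim about impact in a cohort. Sections 1.5.1 and 1.5.3 treat NAS and fibrosis as parallel effects, and the lifestyle study is summarised by separate rates. On that reading Sections 3.2 and 3.3 take the two parts in turn. This stands as a legitimate reading. A reader might infer that no planned result can answer Hypothesis 1. That follows only if both changes must occur in one subject, which the text does not establish. The cohort reading does not remove the gap on worsening, however.

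A reader might also infer that the trial could be declared a success on responders whose fibrosis worsened. The documents set no trial-level success threshold. Such a subject is a responder under Section 3.2, and nothing more can be said.

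The 1-to-9 range is also open to challenge. The 60% is assumed, and a joint count of 1 would need all 8 NAS non-responders to regress but only 1 of the 12 responders. The cited study links weight loss to improvement in all histological features, which points towards the upper part of the range. The range shows what the planned figures leave undetermined, not what is likely.

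Finally, the table could be made at reporting, since nothing forbids it. That is true, but a table chosen after results are known is optional, and the unfavourable cells are the easiest to omit.

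**Conclusion.** The concern holds as a gap in the planned reporting. Hypothesis 1 leaves open whether it is per subject or cohort-level. Section 7 tests mean NAS without producing the Section 3.2 count, and it reports fibrosis in the favourable direction only. On either reading, the planned outputs cannot show the net effect on fibrosis or whether NAS responders worsened. On the per-subject reading they also cannot give the quantity the hypothesis names.

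The size can be stated only as bounds. With 9 of 20 regressing, 0 to 11 may be worse. With 12 NAS responders as well, 1 to 9 have both changes. These rest on an assumed 60% NAS response and on a 45% regression rate taken from a subgroup of another study. The sample size calculation reproduces and is not in question.

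**What to change.** In Section 7:

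- Report the number and percentage of subjects with a NAS improvement of at least 2 points, with an exact 95% interval, so that the endpoint in Section 3.2 has an analysis.
- Cross-tabulate NAS response (yes/no) against fibrosis change (regressed, unchanged, worse). Give the percentage regressed, the percentage worse and the percentage with both NAS response and regression, each with an exact 95% interval.
- Show subjects withdrawn for progression to cirrhosis in the worse category, whether or not they were replaced. If they have no second biopsy, show their NAS response as not assessed.

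In Section 2.1, state which reading of Hypothesis 1 is meant. If per subject, the joint count is its result. If cohort-level, the two separate results are, and the joint count is supportive. Keep Section 3.2 as the primary endpoint. The table has no weight-loss element, so it describes histology and does not by itself establish the association with weight loss.

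The cost is a few sentences and one table, with no new biopsies, visits or subjects. The joint rate can be no higher than the NAS response rate alone, so the sponsor should expect a less favourable figure beside the primary one.
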